11.5.2 Expected AE: Drug

- a) Known risk/Discomforts associated with study Drug.

12.0 Potential challenges and alternative approaches

If we demonstrate poor safety profile of the 6-10ng/ml dose of oral sirolimus, then no further clinical trials of this dose oral sirolimus for treatment of epistaxis in HHT will likely be planned. There may not be an observed effect of this dose oral sirolimus on epistaxis as via PRO-CB based on the number of participants in the study.

13.0 Withdrawal (Stopping) Criteria and Procedures

Subjects may withdraw from the study at any time at his/her own request.

Subjects can be withdrawn from the study by the investigator at any time for any reason and due to the following safety or compliance:

- If continuation in the study appears to be medically harmful
 - Due to evidence of Serious Adverse Events
 - -Adverse Events/Adverse Drug Reaction (unexpected/expected) that are unfavourable and could lead to possible serious adverse events at the discretions of the study investigator
- If it is later discovered that the subject does not meet the eligibility requirements

- If the subject does not follow the instructions for investigational product or follow-up visits
- If the subject becomes pregnant

If a subject is withdrawn from the study or if the study ends early, we will ask subjects to return all leftover study drugs and complete the early termination study visit.

Continued collection and use of data after withdrawal

If a subject withdraw, or are withdrawn from the study, data collected up to that time will still be used. No more data will be collected unless it is necessary to follow up on an adverse event that is not resolved at the time of withdrawal.

Continued use of samples after withdrawal

If a subject decides to leave the study, the subject can request withdrawal of their samples from the research by contacting the study team. The study team will keep and use any research results obtained prior to withdrawal of consent (data from samples that have been analyzed). No further analysis will be done on any remaining samples and the sample will be destroyed.

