5.3.3 Follow-up period

There will be a follow-up period of 3 months post the investigational product period, during which safety and outcome data will be collected.

5.4 Table of Study visit Summary:

*Visit Summary	***Weeks (time Point)	****Blood work (safety) + Biomarkers	Daily Diary (DD)+ Epistaxis severity score (ESS)	Safety and Adverse event Monitoring, Medical history	Tissue biopsy	Pill count
Screening Clinic visit/ ICF	0	Safety	DD+ESS	X	X	
Phone Visit/ baseline period	1,2,4,6,8,1 0		DD	X		
Investigational product assignment/ clinic visit/(day 0)	12	Safety + biomarker	DD+ESS	X		X
**Dose adjustment (as needed)	13	Safety		X		
Phone visit	14,16		DD	X		
Clinic visit (6 weeks investigational product)	18	Safety + biomarker	DD+ESS	X		X
Phone visit	20, 22		DD	X		
Clinic Visit (12 weeks) End of investigational product	24	Safety + biomarker	DD+ESS	X	X	X
Start of Follow-up Period, Phone visit	26, 28, 30, 32, 34		DD	X		
Final Epistaxis daily diary documentation	36	Safety + biomarker	DD+ESS	X		

* Medical History and Physical Examination at all clinical visits..

** a blood sample will be collected for sirolimus blood level, for dose adjustment

*** +/- 7 days, unscheduled clinic visit or safety blood work – will occur if required to assess safety and for women of childbearing potential on effective contraceptive – will occur if required to assess safety and for women of childbearing potential on effective contraceptive.

****safety blood work will include: Electrolytes (Sodium, Potassium, Chloride, total CO₂), Hematology (total blood count-CBC), Renal Function test (urea, creatinine), Liver function (AST, ALT, total Bilirubin), ferritin level, Pregnancy test (BHCG level) and sirolimus blood level, blood glucose level, lipid assessment (total Cholesterol, Triglycerides)

*****Biopsy samples will be collected if the subject have two skin telangiectases of >2mm diameter available for excisional biopsy, prior to the start of study drug and at the end of treatment period.

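### Section 13 ends most data collection for anyone the investigator withdraws, and the protocol describes no way to stop the drug and stay in the study

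*Protocol*

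**What the plan says.** Section 13.0 gives a single exit status, withdrawal from the study. It is discretionary: "Subjects can be withdrawn from the study by the investigator at any time for any reason". The listed grounds include serious adverse events, and other adverse events or drug reactions "that are unfavourable and could lead to possible serious adverse events at the discretions of the study investigator". They also include non-adherence: "If the subject does not follow the instructions for investigational product or follow-up visits".

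The data rule covers both kinds of withdrawal: "If a subject withdraw, or are withdrawn from the study, data collected up to that time will still be used". It continues: "No more data will be collected unless it is necessary to follow up on an adverse event that is not resolved" when the person leaves. The same section asks those leaving to "complete the early termination study visit". The visit table in section 5.4 does not list that visit, and its content is not defined anywhere.

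Other sections expect data after the drug ends. Section 5.3.3 states: "There will be a follow-up period of 3 months post the investigational product period, during which safety and outcome data will be collected". Section 7.2 has the diary running for all 9 months, and Aim 3 in section 3.1 looks at biomarkers on and off therapy. Section 4.2 counts people who take only part of the course towards the target of 10. Section 10.1 describes participants stopping the drug on signs of severe allergy, without saying whether they then leave the study.

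**The concern.** The halt in data collection is not confined to people who refuse further contact. As written, it also covers a willing participant whom the investigator takes out because of toxicity or missed doses. For that person, the reason for leaving and the reason for missing data are the same.

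Section 7.1 makes adverse events the primary outcome, and section 12.0 says a poor safety profile would probably end plans for further trials of this dose. If the late record consists mainly of people who tolerated and adhered to the drug, delayed or new events may be under-detected among those most likely to have them. Sections 4.0 and 4.2 instead name epistaxis reduction as primary. The data loss matters on that reading too, because the diary stops at the same moment.

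An analysis plan can say how missing data are handled. It cannot recover data that the protocol says not to collect.

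**Working it through.** The protocol has no figure of its own to reproduce here: section 8.1 gives a final sample size of 10 with no withdrawal rate. The check is a count of scheduled data against the withdrawal rule.

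**Inputs**
- First dose at week 12 (section 5.2.1) and last scheduled contact at week 36 (section 5.4), so 36 − 12 = 24 weeks of observation after first dose.
- Follow-up period: weeks 24 to 36, or 12 weeks (sections 5.3.3 and 5.4).
- Safety draws after first dose: weeks 13, 18, 24 and 36. Biomarker draws after first dose: weeks 18, 24 and 36 (section 5.4).
- Phone checks after first dose: weeks 14, 16, 20, 22, 26, 28, 30, 32 and 34, nine in all (section 5.4).

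**Loss for one participant withdrawn at week w**

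Diary share lost = (36 − w)/24. This is an upper limit, because it makes no allowance for the early termination visit or for follow-up of an open event.

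| Withdrawn at week | Diary weeks lost | Safety draws lost (weeks) | Phone checks lost |
|---|---|---|---|
| 14 | 22/24 = 92% | 18, 24, 36 | 8 of 9 |
| 18 | 18/24 = 75% | 24, 36 | 7 of 9 |
| 24 | 12/24 = 50% | 36 | 5 of 9 |

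The biomarker draws lost are at the same weeks as the safety draws. The whole 12-week follow-up is lost in every row.

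**Loss across the study**

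The number withdrawn is an assumption. With 10 participants there are 10 × 24 = 240 person-weeks after first dose and 10 × 12 = 120 in follow-up. If k of 10 are withdrawn at week 18:
- k = 1: 18/240 = 7.5% overall and 12/120 = 10% of follow-up.
- k = 2: 36/240 = 15% and 24/120 = 20%.
- k = 3: 54/240 = 22.5% and 36/120 = 30%.

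**Precision, for scale**

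If a late event is never seen among n people followed, the one-sided 95% upper bound on its rate is 1 − 0.05^(1/n). This gives 25.9% for n = 10, 28.3% for 9, 31.2% for 8 and 34.8% for 7. The widening is moderate. The larger problem is selection, because the bound assumes that those still followed resemble those who left.

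**Consistency of the sections**

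Section 4.2 counts people with any partial course. Section 8.0 plans its 10 around at least 18 weeks in the study, which is 18 − 12 = 6 weeks after first dose. Section 13 says data up to withdrawal are used. Someone withdrawn at week 14 fits section 4.2, falls short of the minimum in section 8.0, and still has data that section 13 says to use.

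**The case against.** The rule is milder than a quick reading suggests. Withdrawal is at the investigator's discretion, so an adverse event need not end participation. An event open at withdrawal is still followed, which will cover many people withdrawn for toxicity. Everything collected beforehand is kept, including the triggering event. An early termination visit is requested, and a footnote to section 5.4 allows unscheduled visits and safety blood work. Staying in the study off drug is not described, but it is not forbidden. All of this stands. It limits the loss to later diary entries, scheduled laboratory and biomarker draws not needed for an open event, and detection of new events.

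Three stronger readings are tempting but not supported:
- A reader might infer that those withdrawn for toxicity lose their safety data altogether. The exceptions above rule that out.
- A reader might infer that Aim 2A is biased towards benefit. Lack of benefit is not a listed ground for withdrawal. The comparison is with baseline, and nothing shows that missing later weeks would favour the drug. Whether diary data after stopping drug enter that comparison may be left to an analysis plan.
- A reader might count each withdrawn participant as 10% of the evidence. That does not fit an early withdrawal: someone leaving at week 14 is below the 18-week minimum in section 8.0, and section 4.2 allows up to 20 to be enrolled.

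A reader might also see the early termination visit as contradicting the rule against further collection. It can reasonably be read as a close-out at the moment of leaving. What remains is that its content is undefined.

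**Conclusion.** The point holds in limited form and should be corrected. Section 13 does not separate stopping the drug from leaving the study, and its data rule reaches people who have not withdrawn consent. Withdrawal by the investigator at week 18 would cost up to 75% of the diary weeks after first dose, two scheduled safety and biomarker draws, and surveillance for new events across the whole follow-up.

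The study-level effect is unknown because no withdrawal rate is stated; the figures for 1 to 3 of 10 are illustrative. The direction for safety is clear in kind, since later observation would come mainly from those who tolerated and adhered to the drug, but its size cannot be given. This conclusion assumes that section 13 is followed as written and that investigators use the withdrawal grounds it lists.

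**What to change.** In section 13, separate stopping study drug from withdrawing consent to data collection. Unless consent is withdrawn, participants who stop drug continue the existing diary, phone calls and scheduled visits to week 36. State the content of the early termination visit in section 5.4 and offer it to anyone leaving the study, whatever the reason.

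Reconcile section 13 with section 4.2 on partial courses and with the 18-week minimum in section 8.0. Reconcile it also with the pregnancy text in section 10.1, which ends participation at once yet seeks permission for later monitoring that section 13's single exception does not mention. The criteria for stopping the drug are not touched.

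The cost is a protocol amendment, revised consent wording, and a modest diary and visit burden for people no longer on drug. The calls and visits are already in the section 5.4 schedule.

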14.0 Human Subject Recruitment

The study will be conducted in accordance with ICH Good Clinical Practice (GCP). This will include REB and Health Canada approval to conduct the study and written informed consent from each subject.

Subjects will be recruited as follows:

- 1) All subjects with a confirmed diagnosis of HHT and moderate to severe epistaxis will be approached for participation in clinic.
- 2) Participants will learn about the study through the website:

<https://www1.rarediseasesnetwork.org/cms/bvmc/Get-Involved/Studies>

If they're interested, they can contact the research coordinator for pre-screening for eligibility.

Ten subjects will be recruited. Subjects may or may not benefit directly from inclusion in this study. Knowledge from this study may help doctors better understand treatment for HHT or help determine who is more likely to benefit from the sirolimus treatment. It may also help future patients. However, we hope that at the end of this study, researchers may be in a better position to propose clinical trials that may help reduce vascular malformations in individuals with HHT.

14.1 Risk, Warnings and Precautions:

Related to study drug: Please see Product Monograph GD ® -Sirolimus

(Sirolimus Oral Solution and Tablets) GenMed, a division of Pfizer Canada, April 8, 2021

14.2 Warnings related to test

- a) Blood sample collection: When blood samples are taken from a vein. Discomfort or pain may occur. Participants may feel faint or experience bruising, irritation or redness at the site.

- b) Biopsy: The needle with the freezing may causes a stinging or burning sensation. The freezing can cause nausea. Allergic reaction is unlikely. Bruising may occur, which could last for 2 weeks. There is a small risk of a local skin infection. There is likely to be a small scar at the site of the biopsy. It is much less common to have a raised itchy scar, which could be injected with cortisone to help it flatten. After 7-10 days the (1-2) stitches will be removed.

14.3 Written informed consent

Written informed consent will be obtained from each participant before any study procedure or assessment is conducted. The study will be explained, the nature and purpose, the potential benefits, and possible risks associated with participation in this research study. After all the participant's questions are answered and as much time is give as required by the participant, he/she will be asked to sign and date the informed consent.

14.4 Process of consenting

The study participants will be approached in clinic or by phone (with previous permission given to call). The study coordinator will explain the information in the written informed consent to the participant. The participants will be asked several times if they understood details of the study and if there are questions. The participants will be offered time to read, consider and discuss the study, including taking the consent home for additional time to consider participation. A Qualified Medical Personnel will be available for any medically related questions or concerns. After all questions are answered the participant will be asked if they agreed to participate in this study. The participant will sign and date the informed consent form and a copy will be given to the participant.

14.5 Quality assurance

For the research subject's protection and to ensure compliance with GCP and applicable regulatory requirements, quality assurance assessment and or audits of the site records may be conducted by, Health Canada, National Institute of Health (NIH)). In the event of the assessment or audit direct access to all relevant study documents will be required from the investigator and institution.

14.6 Study Governance

14.6.1 Data safety monitoring plan

The Principal Investigator has appointed a Data Safety Monitoring Board (DSMB), comprising of two physicians and a statistician. The DSMB will convene every six months to review safety data. The DSMB will also convene if necessary to review increased safety events. The DSMB will review the protocol prior to the start of the study. The purpose of the DSMB is to review the protocol and conduct of the study and

provide guidance to the study investigator. The DSMB is a group of experts with relevant knowledge in patient care, the disease (HHT) and in clinical research trial conduct and methodology. The DSMB members will serve in an individual capacity and provide their expertise and recommendations in the conduct of the study.

14.6.2 Study Monitoring

The study Principal Investigator and team will monitor the study according to applicable GCP standards and ICH guidelines to ensure the completeness, correctness, and consistency of the data and to assess whether the study is executed according to this protocol and monitoring plan. Safety monitoring will occur every two weeks and severe adverse events will be reported in compliance with the Unity Health Toronto Research Ethics Board and Health Canada.

16.0 Appendices

16.1 Epistaxis Severity Score (ESS) for Hereditary Hemorrhagic Telangiectasia

The purpose of these questions is to calculate a severity score of epistaxis (nose bleeding) for patients with Hereditary Hemorrhagic Telangiectasia.

Please answer each of the following questions as they pertain to your TYPICAL symptoms **WITHIN THE LAST 3 MONTHS** for nose bleeding. Please answer all questions.

HHT-ESS

1. How often do you TYPICALLY have nose bleeding?

- ☐ Less than once per month
- ☐ Once per month

- ☐ Once per week
- ☐ Several per week
- ☐ Once per day
- ☐ Several per day

2. How long does your TYPICAL nose bleeding last?

- ☐ < 1 minute
- ☐ 1-5 minutes
- ☐ 6-15 minutes
- ☐ 16-30 minutes
- ☐ > 30 minutes

3. How would you describe your TYPICAL nose bleeding intensity?

- ☐ Not Typically Gushing or Pouring
- ☐ Typically Gushing or Pouring

4. Have you sought medical attention for your nose bleeding?

- ☐ No
- ☐ Yes

5. Are you anemic (low blood counts) currently?

- ☐ No
- ☐ Yes
- ☐ I don't know

6. Have you received a red blood cell transfusion SPECIFICALLY for nose bleeding?

- ☐ No

[illegible]

dd/mm/yyyy											
dd/mm/yyyy											
dd/mm/yyyy											
dd/mm/yyyy											

16.3 Wallet Card
